9.6. Deviations from the Original Statistical Plan

Changes to the original statistical analysis plan due to changes to the protocol should be agreed

upon among multiple parties, including the sponsor, investigators, data management and statistical analysis staff, and ethics staff and should be made in strict compliance with clinical trial operating regulations and procedures, and changes will not be made lightly otherwise.

10. Data Management

10.1. Data Management System

The data collection/management system used for this trial corresponds to an electronic data capture (EDC) system. An EDC system that has been systematically validated and has trace management and user rights management has been selected.

10.2. eCRF Design

The data manager will design the eCRF according to the needs of the protocol and each eCRF will contain all the data points specified in the protocol, excluding external data. eCRFs will be directly exported from the corresponding EDC system (in PDF format).

10.3. Data Management Plan

The data manager will draft a DMP based on the finalized protocol, project requirements, etc. It will furthermore be determined after discussion by all parties involved in the clinical trial.

10.4. Data Verification Plan

The data manager will draft a data verification plan based on the clinical trial protocol and eCRFs. It will furthermore be determined after discussion by all parties involved in the clinical trial.

10.5. Electronic Database Construction and Testing

A database builder will construct the database, including configuring logical verification rules, system function settings, etc.; a data administrator will manage rights according to each user's job role(s). Database testing will include entry, export, logical verification, eCRF interface, and system functionality testing.

10.6. Database Training and Formal Launch

Prior to the official launch of the trial database, the data manager will train relevant personnel. The training will include: System operation skill training and/or project requirement training. The specific nature of the training will depend on each participant's responsibilities and previous experience. Database launch: Once the database passes testing and all other preparatory work is

completed and following confirmation by the sponsor, the database will be officially launched.

10.7. Data Verification

Data verification includes source data verification (SDV) conducted by monitors through comparing electronic Case Report Forms (eCRF) with source documents, logical review by the medical team in accordance with the Medical Review Plan, and verification by the data management team in accordance with the verification rules specified in the Data Review Plan. In case of any queries, the personnel responsible for queries may directly issue manual queries in the database. If data violates the system verification rules configured by the data management team in the database, the system will generate automated queries. After the data entry personnel confirm the source data and clarify the queries, the personnel responsible for queries shall confirm the data status and clarification description and may close the query only after confirmation of correctness. This process may be repeated until no data queries remain. The generation and resolution of all queries, as well as all data updates and modifications, will be automatically saved in the system audit trail for reference.

10.8. Medical Coding

Medical terminology included in clinical trial data must be standardized prior to carrying out statistical analysis. Medical codes need to be created systematically or manually, based on a medical code dictionary that is in common use in the field of clinical trials. Data that do not meet the requirements of the selected medical coding dictionary or for which there exist unresolved questions need to be confirmed with a clinical investigator in the form of a data query. Medical coding content may include: Past medical history, concomitant medications and adverse events. The specific requirements for coding are defined in the Data Management Plan.

10.9. External Data Management

When external data exists for the clinical trial, the data manager must develop an external data management plan and plan out the entire process for managing external data during the clinical trial in advance.

10.10. Data Backup

The system will be automatically backed up daily on a data management cloud server.

10.11. Data Review

Data generated during the course of a clinical trial may violate the clinical trial protocol, requiring a clinical data review at the general trial level. Problems identified in the data review can be addressed by taking appropriate measures, such as revising the clinical trial protocol and censoring subject data.

10.12. Locking of Data

At the end of the study, once the database lock list has been reviewed, the principal investigator, sponsor, statisticians, data managers, supervisors, and other relevant personnel will jointly authorize locking of the database. When data errors are discovered after the database is locked, the potential impact of these data errors on the safety and efficacy analyses will be assessed jointly by the principal investigator, sponsor, statisticians, data managers, and related personnel. If there is a significant impact on the above, the stakeholders will co-sign to unlock the database after which data corrections can be made; if there is no significant impact, the errors in question will be documented in corresponding statistical analysis and clinical summary reports.

10.13. Data Management Reports

The data manager will summarize the process by which data management work was performed as well as operational specifications and management quality and thereby draft a data management report.

11. Feasibility Analysis

11.1. Probability of Success Analysis

The investigational device will be manufactured in accordance with the requirements of the medical device quality management system. The trial device was analyzed and evaluated for physical, chemical and biological properties as well as associated risks, and the results of the analysis demonstrated the feasibility and safety of the product; furthermore, all risks were identified as within acceptable limits, with potential clinical benefits outweighing the risks of use and the device was determined to be more beneficial to subjects' health, with the potential to improve their quality of life.

This trial device was tested on animals and complete experimental data were obtained during the animal testing process, with no adverse events reported in animal test results, demonstrating that the product is safe and effective (refer to the Animal Studies Report).

11.2. Probability of Failure Analysis

- Subjects experienced serious adverse events and an excessive level of dropouts;

- Information provided on the label does not effectively provide guidance to the operator;
- Too many subjects were lost to follow-up;

However, the above factors remain under control, and assuming training can improve the level and proficiency of operation, the investigators have also developed a complete test protocol accounting for the specific nature of the trial.

In addition, the clinical institutions undertaking the trial are well endowed with equipment and technical resources, and the clinical trial leadership has excellent clinical experience, so the likelihood of trial failure is low.

12. Clinical Trial Quality Control

In order to ensure the accuracy and completeness of the data in each eCRF, the implementing institution or a designated supervisor must monitor the research center on a regular basis. During each monitoring visit, the data submitted by the center needs to be compared with corresponding raw data. Investigators' compliance with appropriate regulations and research guidelines will also be assessed.

Researchers must ensure that medical documentation is kept properly and remains intact. Research documents should be subject to inspection by the implementing organization and/or regulatory authorities. Supervisors need to confirm that the rights and welfare of subjects are protected, that the research adheres to GCP guidelines, and that the trial protocol is followed.

13. Clinical Trial Ethical Issues and Informed Consent

13.1. Ethical Considerations

This clinical trial is conducted in compliance with the Declaration of Helsinki and applicable national regulations. The investigator is responsible for submitting the clinical trial protocol, informed consent form, and informational materials provided to subjects to the Ethics Committee, in order to obtain an independent approval document for the conduct of the clinical trial. Approval from the Ethics Committee must be obtained before initiation of the clinical trial. Written approval from the Ethics Committee shall be issued to the investigator, who shall then provide a copy of the approval document to the study sponsor. The Ethics Committee's approval document shall be accompanied by a list of all committee members involved in the review and approval, together with their respective roles.

During the clinical study, any issues related to the safety of the clinical study, such as amendments to the clinical trial protocol or the informed consent form, and serious adverse events occurring during the study also must be promptly reported to the Ethics Committee. The completion or early termination of the clinical study must also be reported to the Ethics Committee.

13.2. Trial Protocol Approval

Prior to the clinical study, the investigator shall submit the clinical study protocol, informed consent form and other relevant documents to the Medical Ethics Committee of the hospital where the institution of the clinical study responsible is located. The clinical study may only commence after obtaining approval from the Ethics Committee. Any amendments to the study protocol shall be implemented only after approval by the Ethics Committee. Serious adverse events during the clinical study shall be reported in a timely manner in accordance with GCP requirements.

13.3. Informed Consent Process

It is the responsibility of the investigators to explain the purpose, methods, benefits, and potential risks of the clinical trial to each subject and to obtain an informed consent form signed by each subject of the clinical trial. Informed consent must be obtained from the subject prior to the commencement of any operational procedures associated with the clinical trial. For those subjects who, for any reason, are unable to sign an informed consent form themselves, their guardian or witness must sign the informed consent form. By signing an informed consent form, the subject shall authorize the clinical study monitor/auditor/health investigation organization to verify raw data that has been obtained from the clinical study to determine the reliability of the clinical study data.

14. Provisions for Reporting Adverse Events and Device Defects

14.1. Adverse Events

An adverse medical event that occurs during the conduct of a clinical trial of a medical device, regardless of whether it is related to the investigational medical device.

Any pre-existing disease documented in medical history during the screening period shall not be considered an adverse event unless there is a change in its nature, severity, frequency, or required intervention.

14.1.1. Severity Assessment of Adverse Events

Mild: Symptoms are slight and do not interfere with normal daily activities, generally, no treatment is required, and symptoms are resolved spontaneously.

Moderate: Symptoms are sufficient to cause discomfort and interfere with normal daily activities; treatment may be required.

Severe: Symptoms result in significant discomfort; may lead to subject withdrawal from the trial; may result in discontinuation of treatment with the investigational device; specific treatment is required.

14.1.2. Causality Assessment between Adverse Event and Investigational Medical Device

1.Relatedness to the investigational product:

Related to the investigational medical device: (1) There is a reasonable temporal relationship. (2) The event is a known risk of the device or can be explained by its mechanism of action. (3) The injury improves or resolves after cessation of device use. (4) The injury recurs upon rechallenge with the device. (5) The event cannot be explained by other confounding factors. If all five criteria are met, the relationship is assessed as "Definite"; if at least two criteria are met, it is assessed as "Possible".

Not related to the investigational medical device: (1) There is no reasonable temporal relationship. (2) The event type cannot be caused by the investigational medical device. (3) The event can be explained by concomitant devices/medications, disease progression, or other therapeutic interventions. (4) Definitely Not Related: All 3 criteria are satisfied. (5) Probably Not Related: At least 1 criterion is satisfied.

2. Relatedness to the procedure:

Definitely related: The reaction is consistent with the known reaction profile of the procedure.

Probably related: The reaction is consistent with the known reaction profile of the procedure; the patient's clinical condition or other treatments may also contribute to the reaction.

Probably unrelated: The reaction is poorly consistent with the known reaction profile of the procedure; the patient's clinical condition or other treatments may account for the reaction.

Definitely unrelated: The reaction is inconsistent with the known reaction profile of the procedure; the patient's clinical condition or other treatments can fully explain the reaction; the reaction resolves upon improvement of the underlying disease or discontinuation of other treatments,

and reappears following reintroduction of such other treatments.

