8.1.7. Secondary Safety Endpoints

- (1) Rate of conversion to thoracotomy or secondary intervention. Whether subjects require

conversion to open thoracic surgery or secondary interventional procedures due to new-onset aortic dissection caused by the index procedure.

- (2) Rate of major adverse events occurring within 30 days after surgery. Refers to all-cause mortality, myocardial infarction, ischemic stroke or respiratory failure occurring within 30 days after surgery. More specifically, myocardial infarction refers to a drastic reduction or complete interruption of the coronary blood supply due to coronary artery disease, resulting in severe and prolonged acute ischemia of the corresponding myocardium, leading to necrosis of cardiomyocytes. Ischemic stroke refers to the end result of necrosis of brain tissue caused by narrowing or occlusion of the arteries supplying blood to the brain or insufficient blood supply to the brain. Respiratory failure is defined as a state resulting in significantly prolonged intubation, tracheotomy, deterioration of lung function, or other fatal outcomes.
- (3) Rate of aortic aneurysm-related mortality at 12 months post operation. Refers to mortality caused by a ruptured aortic aneurysm or endovascular interventional treatment.
- (4) Incidence of severe adverse events. Refers to an event that occurs during the clinical trial that results in mortality or serious deterioration in patient health, including a fatal illness or injury, a permanent defect in body structure or body function, or an event that requires medical or surgical intervention to avoid one or more permanent defects in body structure or body function.
- (5) Incidence of device-related adverse events. Device-related adverse events refer to an adverse medical event related to the use of a device that occurs during the course of the clinical trial. However, a distinction should be made with respect to normal postoperative stress response, such as fever and chest and back discomfort, which, in the judgment of the investigator, need not be recorded as an adverse event. Recording device-related adverse events will be applicable for conditions that are deemed by the investigator to be definitely related, possibly related, or of indeterminate relationship, to the test device.

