4) Secondary Endpoints

Technical success immediately post-procedure, aortic aneurysm progression control rate, incidence of Type I or Type III endoleak, incidence of aortic stent graft migration, postoperative patency rate of branch vessels, incidence of conversion to open thoracic surgery or secondary interventional procedure, major adverse event rate within 30 days post-operation, aortic aneurysm-related mortality at 12 months post-operation, incidence of serious adverse events, and incidence of device-related adverse events.

Statistical description shall be performed for secondary efficacy indicators, with frequencies and percentages calculated. FAS (Full Analysis Set) and PPS (Per Protocol Set) analyses shall also be conducted.

Statistical description shall be performed for secondary safety indicators, with frequencies and percentages calculated. The SS (Safety Set) analysis shall be adopted as the primary approach.

The Kaplan-Meier method shall be used to estimate the survival rate and its 95% confidence interval, with Kaplan-Meier curves plotted accordingly.

Descriptive statistical analysis shall be performed for the changes of all laboratory parameters before and after the trial. All adverse events occurring during the trial shall be recorded in detail; descriptive statistical analysis of adverse events shall be conducted with a list attached.

In addition to the above statistical methods, detailed and additional exploratory analyses may be required, which shall be confirmed in the Study Report and Statistical Analysis Plan (SAP)..

9.5. Statistical methods for all data, including the handling of missing, unused or erroneous data (including premature discontinuation and withdrawal) and inconsistent data.

A Statistical Analysis Plan (SAP) shall be developed prior to study initiation. After database lock, statistical analysis shall be performed in accordance with the SAP, and a statistical analysis report shall be generated based on the results.

(1) Handling of missing data: Missing data shall be handled according to the analysis set in which they are included. Missing data for the primary endpoint in the Full Analysis Set (FAS) shall be classified by reason as follows:

Missing data clearly due to unsatisfactory efficacy: loss to follow-up or missing primary efficacy data resulting from adverse events, death, etc., related (or possibly related) to the investigational device or aortic dissection.

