21.2. Responsibilities of the Ethics Committee

(1) The Ethics Committee shall be responsible for protecting the legitimate rights, interests and safety of subjects, and safeguarding their dignity.

(2) The Ethics Committee shall comply with the ethical principles of the Declaration of Helsinki (World Medical Association) and relevant laws and regulations. The composition, operation and filing management of the Ethics Committee shall meet the requirements of the health administration department.

(3) All members of the Ethics Committee shall receive training in ethical knowledge, these Regulations and relevant laws and regulations, be familiar with the ethical principles and relevant laws and regulations for medical clinical trials and abide by the working procedures of the Ethics Committee.

(4) The Ethics Committee shall review the ethical acceptability and scientific validity of the medical device clinical trial.

(5) The Ethics Committee shall conduct follow-up oversight of the medical device clinical trial. If it finds that the rights, interests and safety of subjects cannot be guaranteed, it may require in writing the suspension or termination of the clinical trial at any time.

(6) The Ethics Committee shall review safety information such as serious adverse events occurring at the trial site reported by investigators, and safety information such as investigational device-related serious adverse events reported by the sponsor. The Ethics Committee may require amendments to the clinical trial protocol, informed consent form and other information provided to subjects, or suspend or terminate the clinical trial.

(7) The Ethics Committee shall review the potential impact of deviations from the clinical trial protocol on the rights, interests and safety of subjects, or on the scientific validity and integrity of the medical device clinical trial.

(8) During the medical device clinical trial, amendments to documents such as the clinical trial protocol and informed consent form, as well as resumption of a suspended clinical trial, may be implemented only after written approval has been obtained again from the Ethics Committee.

(9) The Ethics Committee shall retain all records of ethical review, including written review

records, member information, submitted documents, meeting minutes and relevant correspondence records.

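### The device-causality classes in section 14.1.2 overlap and lack the indeterminate rating that secondary safety endpoint (5) counts, so the device-related adverse event rate is ambiguous by the number of such events

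*Protocol*

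**What the plan says.** Protocol section 14.1.2 gives two separate lists for the relation of an event to the device.

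- **Related list, five criteria.** The first is "There is a reasonable temporal relationship" and the second is "The event is a known risk of the device or can be explained by its mechanism of action". The others are improvement once device use ends, recurrence on re-exposure, and absence of another explanation. On the ratings: "If all five criteria are met, the relationship is assessed as" Definite, and "if at least two criteria are met, it is assessed as" Possible.
- **Not-related list, three criteria.** No reasonable timing; an event type that the device cannot cause; and an explanation by accompanying devices or drugs, disease progression or other therapy. All three give Definitely Not Related. For the weaker rating the rule is "Probably Not Related: At least 1 criterion is satisfied".

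No sentence says which list prevails when both are met.

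Three other places use the relation to the device:

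- Section 8.1.7(5), repeated in the Trial Protocol Summary, counts an event as device-related when the investigator deems it "definitely related, possibly related, or of indeterminate relationship, to the test device".
- Section 9.5 puts missing primary-endpoint data in its first category, always imputed as failure, when the cause is "related (or possibly related) to the investigational device or aortic dissection". Causes unrelated to either go to the second category, which gets best-case, worst-case and tipping-point runs.
- Section 21.2(6) has the ethics committee review "investigational device-related serious adverse events reported by the sponsor".

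**The concern.** A rating scale that feeds an incidence endpoint should put each event in exactly one class, and its classes should be the ones the endpoint names. Section 14.1.2 does neither. Two investigators can both follow the protocol to the letter, rate the same event differently, and so place it inside or outside endpoint (5). An event that cannot be judged has no rating of its own, although the endpoint expects one. It has to be forced into one of four classes, two of which are not counted.

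The rule is applied at the site when the event is recorded. An analysis plan written later could not recover consistent ratings from events coded under conflicting rules. At stake is the clarity of a named secondary safety endpoint in a pre-market, single-arm study and, to a small extent, the missing-data runs of 9.5.

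**Working it through.** **Denominator.** Section 8.1.4.8 gives 72 valid cases and 20% dropout: 72 / (1 − 0.20) = 90. The plan's figure is reproduced. It serves only as the denominator below.

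**Step 1: one event, two ratings.** Take an event with reasonable timing, a recognised device risk, and a competing explanation such as disease progression.

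| Question | Related list | Not-related list |
|---|---|---|
| Reasonable timing? | criterion 1 met | criterion 1 not met |
| Known risk or mechanism? | criterion 2 met | criterion 2 not met |
| Another explanation? | criterion 5 not met | criterion 3 met |
| Number met | 2 of 5 | 1 of 3 |
| Rating | Possible | Probably Not Related |
| Counted in endpoint (5)? | yes | no |

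Both thresholds are reached. This is a realistic pattern, because section 8.1.2 describes the enrolled patients as generally of advanced age with severe comorbidities.

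**Step 2: does the overlap depend on one contrived case?** List every met/not-met pattern under this coding:

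- not-related 1 is the negation of related 1;
- not-related 3 is the negation of related 5;
- not-related 2 cannot hold when related 2 holds, but both may fail.

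That gives 16 patterns with related 2 met and 32 without it, 48 in all.

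| Outcome | All 48 patterns | 12 patterns with related 3 and 4 not met |
|---|---|---|
| Possible and Probably Not Related | 28 | 3 |
| Possible and Definitely Not Related | 1 | 0 |
| Possible only | 7 | 2 |
| Definite only | 1 | 0 |
| A not-related rating only | 11 | 7 |

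The right-hand column assumes that a permanently implanted graft cannot be withdrawn or reintroduced. No Definite rating is then reachable, so the counted events rest on Possible, which is the class that overlaps. These counts show that the overlap is built into the rules. They are not event frequencies.

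**Step 3: the indeterminate class.** Section 14.1.2 has four device ratings, and no pattern produces a fifth. Under the same coding nothing is left over either: if no not-related criterion holds, related 1 and 5 both hold, so the event is at least Possible. The class that 8.1.7(5) counts therefore has no route by which an event can enter it.

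**Step 4: size.** Let k be the number of subjects whose only candidate device-related event is an overlap or unassessable event. The rate can be read k/N apart. With N = 90, one subject gives 1/90 = 1.1 percentage points; k = 5, an assumed illustration, gives 5/90 = 5.6 points. With N = 72, one subject gives 1/72 = 1.4 points. The protocol gives no basis for k.

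**Step 5: reach into section 9.5.** A subject moved from the first to the second category is still a failure in the worst-case run, so that result does not change. The best-case and tipping-point runs can change. They do so only where the category turns on the device; section 9.5 also turns on aortic dissection, which 14.1.2 does not rate. A known death is already a primary-endpoint event.

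**The case against.** The strongest reply is that little depends on this. Endpoint (5) is described by frequencies and percentages with no test (9.4.2). The primary endpoint, all-cause death or major stroke, needs no causality rating. All adverse events are recorded in detail and listed, so a reader can reclassify them. The endpoint's wording is also inclusive: an investigator facing both lists would most naturally call the event possible or indeterminate, and both are counted.

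Most of this stands as a limit on the consequence. The last part is an inference, because the protocol states no such preference and the rule for Probably Not Related is just as explicit. The procedure scale in the same section shows that the case can be handled: there, a consistent reaction to which the patient's condition or other treatment may contribute is still rated probably related. The device scale has no equivalent.

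A reader might infer more than the documents support:

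- **That the device-related rate is wholly undetermined.** Events meeting only one list are rated without conflict; the doubt is confined to overlap and unassessable events.
- **That 14.1.2 decides the missing-data category.** Section 9.5 does not cite those ratings and has its own aortic dissection limb.
- **That serious adverse events could go unreported.** Section 14.4.2 requires reporting whether or not the event is related to the device. At most the label under which an event reaches the ethics committee under 21.2(6) changes.
- **That the ambiguity favours the device.** It allows over-attribution as readily as under-attribution.

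**Conclusion.** The point holds in limited form. The rules conflict as written: the same event can belong to a counted and an uncounted class, and the endpoint names a class that the scale cannot produce. The effect on the device-related adverse event rate is 1.1 percentage points per affected subject at N = 90, in either direction. The number of affected subjects is unknown, so no overall size can be given.

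The overlap follows directly from the text. The pattern counts also rest on the coding in Step 2 and, for the 12-pattern version, on the assumption about a permanent implant. The primary endpoint definition and the duty to report serious adverse events are untouched, and the worst-case run in 9.5 is the same under either category. This is a drafting contradiction worth removing because it feeds a named safety endpoint, not a threat to the trial's main conclusion.

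**What to change.** Make the 14.1.2 classes mutually exclusive and exhaustive by stating a precedence. For example: an event meeting two or more related criteria is at least Possible, and both Probably Not Related and Definitely Not Related apply only when fewer than two related criteria are met. The restriction must cover both not-related ratings, since one pattern in Step 2 is Possible and Definitely Not Related at once.

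Under the Step 2 coding this leaves each of the 48 patterns in one class: 28 + 1 + 7 + 1 = 37 Possible or Definite, and 11 not related. In the 12-pattern version it is 3 + 2 = 5 Possible and 7 not related. Another precedence would also remove the conflict; the documents do not dictate this one.

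In addition:

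- add an Indeterminate rating in 14.1.2 for events that cannot be assessed, with an eCRF code;
- state in 8.1.7(5) and the Trial Protocol Summary that Definite, Possible and Indeterminate are counted;
- use the same terms for the device limb of the two missing-data categories in 9.5, and say separately how relation to aortic dissection is judged.

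The cost is a few lines of text and one eCRF code, but section 15.3 requires ethics approval for any change to the protocol or case report form. The reported device-related event rate may be somewhat higher.
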